4.3 Interim analyses and data monitoring

sudy to support regulatory submissions. At a minimum, 2 interim reports are planned after all enrolled Japanese subjects complete through Visit 5 (Week 24) and after all enrolled Japanese subjects complete through Visit 7 (Week 48). All analyses described in this SAP will be presented at each interim analysis for regulatory reporting

4.4 **Multicenter studies**

Descriptive summaries for individual sites will not be presented due to the low number of expected subjects per site. However, subject data listings will provide data grouped by country and individual site.

4.5 Multiple comparisons/multiplicity

This section is not applicable.

Use of an efficacy subset of subjects 4.6

Selected efficacy analyses will be performed for the completer cohorts defined in Section 3.2.3.

Examination of subgroups 4.7

Unless otherwise noted, all tabular data summaries will be presented overall and by country (Japan, China).

STUDY POPULATION CHARACTERISTICS 5

5.1 Subject disposition

Summary tables of subject disposition will be provided overall, by EP0008 randomized dose and by country separately as follows:

- The number of subjects in the SS, and in the FAS will be presented. The date of the first visit for the first subject, date of the last visit for the last subject, and the number of subjects screened will also be included. (Analysis population: All Subjects Screened)
- The number and percentage of subjects entering, completing, ongoing, and discontinuing the study with associated reasons for discontinuation. The number and percentage of ongoing subjects will be displayed at the interim analyses only. (Analysis population: SS and FAS)
- A by-subject listing of analysis population classification (Analysis population: SS)

The following listing will be provided:

Subject disposition status, including the date of informed consent, screening result, date of study completing/discontinuation, and reason for premature discontinuation. (Analysis population: SS)

A by-subject listing of subjects who did not meet study eligibility criteria (Analysis population: All Subjects Screened)

Confidential Page 13 of 35 A by-subject listing of analysis population classification (Analysis population: SS)

5.2 **Protocol deviations**

A summary table and listing of important protocol deviations will be provided for the SS as follows:

- The number and percentage of subjects with no important protocol deviations and with at least 1 important protocol deviation in each of the categories defined in Section 3.4 will be summarized overall, by EP0008 randomized treatment.
- A by-subject listing of important protocol deviations will be presented.

6 **DEMOGRAPHICS AND OTHER BASELINE CHARACTERISTICS**

Unless otherwise specified, demographics, baseline characteristics, medical history, concomitant disease, and concomitant medications will be summarized for the SS and FAS overall, by EP0008 randomized treatment group, and by country separately.

Subject listings of demographics, baseline characteristics, medical history, concomitant diseases, and concomitant medication will be displayed for the SS.

6.1 **Demographics**

Summary statistics or the number and percentage for each category of demographic information will be presented as follows:

- A summary of demographics data including gender, age (years), age category (≤ 18 , >18 to $<65, \ge 65$ years) ($<16, \ge 16$ to $<65, \ge 65$ years), ethnicity (Hispanic or Latino, and not Hispanic or Latino), race group (American Indian/Alaskan native, Asian, Black, Native Hawaiian or other Pacific Islander, White, and Other/mixed), race, racial subgroup (Chinese or Japanese), height, weight, body mass index (BMI, kg/m²), BMI category (<18.5, ≥18.5 to <25, ≥25 to <30, and $\ge 30 \text{ kg/m}^2$), number of lifetime AEDs, number of concomitant AEDs during EP0008, and Baseline partial-onset seizure frequencies per 28 days will be provided overall. by EP0008 randomized treatment group, and by country separately.
- A by-subject listing of demographic data.

Gender, race, ethnicity, racial subgroup, height, weight, and BMI will betaken directly from EP0008 datasets and not programmed. Age will be relative to the date of informed consent for EP0009.

Other Baseline characteristics 6.2

Summary statistics or the number and percentage for each category of baseline characteristics as reported at Visit 1 of EP0008 will be provided as follows:

A summary of the diagnoses of primary disease, including time since diagnosis of epilepsy (in years) and etiology of epilepsy taken from EP0008 will be provided.

In EP0008, time since first diagnosis was calculated using all available information; partial dates was completed using the earliest calendar date based on the partial date provided.

Confidential Page 14 of 35 In EP0008, time since the first diagnosis (years) was calculated as (year and month of informed consent date – year and month of the first diagnosis) / 365.25. Month and year of the first epilepsy diagnosis are collected on the CRF. To calculate the time since first epilepsy diagnosis at Visit 1 of EP0008, a complete date will be imputed as follows:

- Missing the month, but year present assign January 1st of the year, the subject's birthday, or the date birthday, or the date of the first seizure, whichever is later in the year. Both month and year are missing, no imputation will be a subject of the year.
- A summary of International League Against Epilepsy (ILAE) seizure classification will be provided.

The types of partial seizures experienced will be summarized using the ILAE classification system.

- A summary of classification of epileptic syndromes.
- A by-subject listing of other Baseline characteristics.

6.3 Medical history and concomitant disease

Medical history and concomitant diseases will be as reported as of Visit 1 of EP0008.

Concomitant diseases are medical history events which were ongoing at Visit 1 of EP0008.

Summary tables of medical history and concomitant diseases will be provided for the SS as follows:

- A summary of medical history by MedDRA system organ class (SOC) and preferred term (PT) will be presented overall, by EP0008 randomized treatment group, and country separately.
- A summary of concomitant disease by MedDRA system organ class (SOC) and preferred term (PT) will be presented overall, by EP0008 randomized treatment group, and country separately.
- A by-subject listing of medical history.
- A by-subject listing of concomitant diseases.
- A by-subject listing of procedure history.

Concomitant medications

Concomitant medications will be defined as any medications taken concurrent with LCM if the start date was prior to the first dose with ongoing status, or the start date was on or after the date of first dose of study drug in EP0009. Medications with a missing start date, whose stop date is either unknown or after the date of the first dose of study drug, will be considered concomitant.

Summary tables will be provided for the SS and FAS as follows:

A summary of concomitant medications (excluding AEDs) taken during Treatment Period will be provided by level 1 and level 2 ATC code. The tables will be presented overall, by EP0008 randomized treatment group, and by country separately.

- A summary of concomitant AEDs taken during the Treatment Period will be provided by Level 4 ATC code and preferred medication name. The tables will be presented overall, by EP0008 randomized treatment group, and by country separately.
- A by-subject listing of concomitant AEDs (Analysis population: SS)
- A by-subject listing of concomitant medications (non-AEDs) (Analysis population: SS)

8.3 Clinical laboratory evaluations

For continuous laboratory measurements, including hematology, clinical chemistry, and urinalysis, a summary using descriptive statistics of the actual values and their change from Baseline (where Baseline is from the previous trial as defined in Section 3.3) will be presented at each visit, the last visit value, the minimum value, and the maximum value during the Treatment Period. For white blood cell differentials, both of absolute values and percentages of the white blood cell count will be analyzed. When analyzing categorical data, the number and percentage of subjects in each category will be presented. In addition, shift tables will be used to evaluate the number and percentage of subjects having a different Treatment Period status (low, normal, and high) when compared to their baseline status from EP0008.

Repeated or unscheduled laboratory assessments during the study will not be presented for each visit summary, but will be considered when determining the last visit value, minimum value, and maximum value during the Treatment Period and when determining treatment emergent marked abnormality.

Categorical urinalysis parameters (excluding urine glucose, urine ketones, and urine protein) will be presented in listings only.

The number and percentage of subjects with treatment-emergent marked laboratory abnormalities (hematology and clinical chemistry) as defined in Section 13 will be summarized by laboratory parameters. Treatment-emergent is defined as meeting the marked abnormality criteria during EP0009 Treatment Period but not meeting the criteria during Baseline of EP0008. Subject numbers for subjects meeting the marked abnormality criteria will also be presented.

A subject data listing will be provided for all laboratory data. Values outside the normal range will be flagged within the listing. A subject data listing will also be provided for all treatment-emergent marked laboratory abnormalities and will include all lab values for those subjects experiencing the marked abnormality.

The following summaries and listings will be provided:

- A summary of each laboratory parameter and change from Baseline of EP0008.
- A shift table based on the normal range for each lab parameter will be presented by Treatment Period endpoint value relative to Baseline of EP0008.
- A summary of incidence of treatment-emergent marked abnormalities presented by scheduled visit and for the entire Treatment Period (including unscheduled visits) during the Treatment Period for the laboratory parameters, hematology and clinical chemistry.

A shift table that will cross-tabulate Baseline value of EP0008 by maximum value during the Treatment Period (including unscheduled visits) will be presented for liver function tests (LFTs) which include alanine aminotransferase (ALT), aspartate aminotransferase (AST), GGT, ATL, and total bilirubin based on abnormality.

The shift table that cross-tabulates Baseline versus maximum values during the Treatment Period in categories of <1 x ULN, 1 to <2 x ULN, 2 to <3 x ULN, ≥3 x ULN, and missing will be presented for the liver function tests.

The summaries above will be provided overall, by EP0008 randomized treatment group, and by country separately.

• A by-subject listing of subjects with laborators.

- A by-subject listing of LFTs with pre-defined criteria.

Vital signs, physical findings, and other observations related to 8.4 safety

Vital signs 8.4.1

Noninvasive pulse rate, systolic blood pressure, and diastolic blood pressure will be measured at visits with the subject in a sitting position after at least 3 minutes at rest, according to the tabular schedule of study procedures in the protocol. Summary statistics of the actual measurement and their changes from Baseline will be presented at each visit, the last visit value, the minimum value, and the maximum value during the Treatment Period

Repeated or unscheduled vital sign assessments during the study will not be presented for each visit summary, but will be considered when determining the last visit value, minimum value, and maximum value during the Treatment Period and post-Baseline abnormal vital signs during Treatment Period.

The following summaries and a listing will be provided:

- A summary of observed blood pressure and pulse rates and changes from Baseline of EP0008.
- The number and percentage of subjects with post-Baseline abnormal vital signs during Treatment Period as defined in Section 13.

The summaries above will be provided overall, by EP0008 treatment group, and by country separately.

A by-subject listing of vital signs. Abnormal vital signs will be flagged in the listing.

8.4.2 Electrocardiograms

For quantitative ECG measurements (heart rate, RR interval, PR interval, QRS duration, QT interval, and corrected OT intervals using Bazett and Fridericia methods), summary statistics of the actual measurement collected at Baseline and each Treatment Period visit (as well as change from Baseline) will be presented. Baseline is defined as the average of the 3 ECG measurements taken at Visit 3 in EP0008. In addition to Baseline and each Treatment Period visit, the last visit, minimum, and maximum values during the Treatment Period of EP0009 will be presented. Repeated or unscheduled ECG assessments during the study will not be presented for each visit summaries, but will be considered when determining the last visit value, minimum value, and maximum value during the Treatment Period and abnormal ECG values.

The Bazett corrected QT (QTcB) will be calculated as

QTcB =
$$\frac{QT}{\sqrt{RR}}$$
, where RR = 60/HR.

The Fridericia corrected QT (QTcF) will be calculated as

$$QTcF = \frac{QT}{\sqrt[3]{RR}}$$
, where $RR = 60/HR$

The following summaries and listings will be provided for the SS:

- A summary of ECG measurements (heart rate, RR interval, PR interval, QRS duration, QT interval, and corrected QT intervals using Bazett and Fridericia methods) and changes and Baseline of EP0008.

 The number and percentage of and or and or
- and an increase from Baseline of <30ms, 30 to <60ms, and ≥60ms will be summarized for each visit.
- The number and percentage of subjects with a maximum QTc of 500ms, a maximum increase in QTc from Baseline of <30ms, 30 to <60ms, and ≥60ms, a maximum post-Baseline OTc of >500ms or a maximum increase in OTc of >60ms, and a maximum post-Baseline QTc of ≥500ms and a maximum increase in QTc of ≥60ms will be summarized for each of the corrected QT interval formulas. Subjects with a QTc (Bazett and Fridericia) of ≥500ms or an increase from Baseline of ≥60ms will be listed.
- The number and percentage of subjects with PR interval values >200ms, >220ms, or >250ms, and the number and percentage of subjects with ORS interval values >100ms, >120ms, and >140ms will be presented. For these defined criteria, the number and percentage of subjects with treatment-emergent PR interval and/or QRS interval prolongation will also be presented. Treatment-emergent is defined as meeting the criteria at any Treatment Period visit (including unscheduled visits) during the Treatment Period and not meeting the same criteria during Baseline.
- Subject numbers for subjects with prolonged post-Baseline QTcB will be provided.
- Subject numbers for subjects with treatment-emergent PR interval prolongation will be provided.
- Subject numbers for subjects with treatment-emergent QRS interval prolongation will be provided.
- A summary of incidence of treatment-emergent abnormality 12-lead ECG findings after start of study drug for each visit and during the Treatment Period in EP0009.

The summaries above will be provided overall, by EP0008 randomized treatment group, and by country separately.

- A by-subject listing of 12-lead ECG data.
- A by-subject listing of abnormal 12-lead ECG data as defined in Section 13.

8.4.3 Other safety variables

Body weight will be determined without shoes when the subject is wearing light clothing, and will be assessed according to the tabular schedule of study procedures.

The following summaries and listings will be provided:

- A summary of body weight and change from Baseline for each visit

the Treatment Period as defined in Section 13.

The summaries above will be provided overall, by EP0008 randomized treatment group, and by country separately.

• A subject listing of body weight and change from Baseline in body weight

• A subject listing of abnormal physical examination abnormalities

• A subject listing of neurological examination findings

• A subject listing of pregnancy test

• A subject listing of C-SSRS suicidality

9 EFFICACY ANALYSES

All efficacy variables are to be evaluated descriptively using FASION

9.1 Statistical analysis of the primary efficacy variables.

No primary efficacy variables are defined for EP0009.

Statistical analysis of the secondary efficacy variables 9.2

Partial-onset seizure frequency per 28 days will be calculated as ([number of seizures over the specified interval] divided by [number of days in the interval]) multiplied by 28.

The following table and listing will be provided:

If a seizure cluster is reported, it will be assigned to the correct seizure type and the highest recorded daily number of seizures of that seizure type during the 28 days prior to the cluster event will be used as the imputed number of seizures for the day on which the cluster occurred. If no other seizures are recorded for that seizure type for the subject in the 28 days prior to the cluster event, the frequency will be set to 1 or the number of cluster episodes reported if more than 1 cluster event occurred on the same day.

9.2.1 Percent change in seizure frequency from Baseline to the Treatment Period

The percent change in partial-onset seizure frequency per 28 days from Baseline to the Treatment Period in 6-month interval is calculated by the following formula:

[(Seizure frequency per 28 days in 6-month interval during the Treatment Period) -(Seizure frequency per 28 days during Baseline Period)] x 100 (Seizure frequency per 28 days during Baseline Period)

Confidential Page 21 of 35 Descriptive statistics will be calculated for the percent change in partial-onset seizure frequency per 28 days from Baseline to the Treatment Period in 6-month specified interval during the Treatment Period, and overall.

The percent change in 28-day seizure frequency per 28 days from Baseline among each completer cohort will also be displayed. A subject must have been treated with LCM and have available seizure diary data for the interval for each interval (eg, 6-month completer cohort subjects must be enrolled and taking trial medication for at least 6 months and have available seizure diary data for the interval) to be included in the 6-month completer cohort (see Section 3.2.3 for definition of completer cohort).

- A summary of the percent change in partial-onset seizure frequency per 28 days from Baseline will be presented by 6-month interval and overall Treatment Period.
- A summary of the percent change in partial-onset seizure frequency per 28 days from Baseline among each complete cohort will be presented. For each completer cohort, the percent change in 28-day seizure frequency per 28 days from Baseline will be presented by 6-month time interval..

The summaries above will be provided overall, by EP0008 randomized treatment group, and by country separately.

• A by-subject listing of number of seizure, seizure frequency per 28 days and percent change from Baseline by 6-month interval and overall Treatment Period.

9.2.2 Response to treatment of at least 50% from Baseline to the Treatment Period

 \geq 50% responders are defined as subjects who experience a \geq 50% reduction in partial-onset seizure frequency per 28 days from Baseline to the 6-month interval or the Treatment Period which is defined at Section 9.2.1.

- The number and percentage of \$50% responders in the partial-onset seizure frequency per 28 days from Baseline to the Treatment Period by 6-month interval and overall Treatment Period will be presented.
- The number and percentage of $\geq 50\%$ responders among each completer cohort will be presented in a same way as above. For each completer cohort, the $\geq 50\%$ response rate will be presented by 6-month time interval.

The summaries above will be provided overall, by EP0008 randomized treatment group, and by country separately.

• A by-subject listing of ≥50% responder categories by 6-month interval and overall Treatment Period.

9.3 Analysis of other efficacy variables

9.3.1 Response to treatment of at least 75% from Baseline to the Treatment Period

≥75% responders are defined as subjects who experience a ≥75% reduction of in the partial-onset seizure frequency per 28 days from Baseline to the 6-month time interval or the Treatment Period.

Confidential Page 22 of 35

- \geq 75% responders will also be summarized by the same manner as \geq 50% responders, described in Section 9.2.2.
- The number and percentage of ≥75% responders in the partial-onset seizure frequency per 28 days from Baseline to the Treatment Period by 6-month interval and overall Treatment Period will be presented.
- The number and percentage of \geq 75% responders among each completer cohort will be presented in a same way as above.

The summaries above will be provided overall, by EP0008 randomized treatment group, and by country separately.

• A by-subject listing of ≥75% responder categories by 6-month interval and overall Treatment Period.

9.3.2 Seizure-free status

A seizure-free status will be assessed for the duration of at least consecutive 6 months (182 days) and at least consecutive 12 months (365 days). Seizure-free is defined as a report of no seizures in the seizure diary on the CRF for the consecutive days where the subject was treated with LCM. Days in the seizure diary which are marked as "not done" on the CRF will not be counted as a seizure free day unless otherwise noted.

When subjects are in EP0024, the days should be treated as "not done" days for EP0009 but they should not disqualify a subject from being seizure free if they were in EP0024.

- The number and percentage of subjects who achieved seizure-free status (yes/no) for the duration of at least 6 months and at least 12 months will be presented overall, by completer cohort, by EP0008 randomized treatment group, and by country separately.
- A by-subject listing of seizure freedom data.

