At selected sites, Japanese subjects may participate in an additional study (EP0024) with the intravenous formulation of LCM without withdrawing from EP0009. The study period of EP0024 will be included in that of EP0009. Subjects will continue to receive their current dose of LCM at the time of entry and remain stable for the duration of EP0024. Subjects who complete or withdraw from EP0024 will be given the opportunity to resume their participation in EP0009 with oral LCM treatment. In the event that a subject withdraws from EP0024 and is required to taper off LCM, the subject will return to EP0009 and taper using LCM tablets. Adverse events and concomitant treatment(s)/medication(s) that occur or were administered during EP0024 will be recorded in EP0024. Ongoing AEs and concomitant medication(s)/medical procedure(s) originating from the EP0024 will be followed in EP0009 until resolution or until stable. Where possible, data updates related to the resolution of ongoing AEs and concomitant medication(s)/medical procedure(s) from EP0024 will be reported in the EP0024 database (eg, updates are made in the EP0024 databases until the database is locked). All other data reported for EP0024 will be captured in the EP0024 database. Per the EP0024 protocol, the study (EP0024) will require hospitalization. Hospitalization for study participation does not need to be reported as an SAE.

Determination of sample size

No formal sample size determination has been performed because EP0009 is an extension study. Approximately 378 subjects, ie, 70% of subjects who were randomized in EP0008, are anticipated to participate in this extension study.

Confidential Page 8 of 35

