- Missing end day, but month and year present: The end day will be set to the last day of the month.
- Missing end day and month, but year present: The end day and month will be set to the maximum of the date of study or the date equivalent to 30 days after last intake of study treatment.
- End date is completely unknown: The end date will not be imputed.

However, if the study termination year and year for the date which is 30 days after last intake of study treatment are greater than the event/concomitant medication year, the day and month are to be set to December 31st.

Relative day is not calculated for partial dates in cases where relative day is shown in a subject listing. In such cases, relative day should be left blank in the subject data listings.

Subjects participating in EP0024 while also enrolled in EP0009 will have missing data for seizure frequency and drug dosing while participating in the EP0024 trial. As the duration of the EP0024 study will be short (3-7 days), no imputation for data missing due to participation in EP0024 will be performed. Subjects will be assigned the same dose in EP0024 as that assigned in EP0009 for the two weeks prior to the start of EP0024. As such, time during the EP0024 study will not be subtracted from the exposure calculations (eg, exposure will be from the start of LCM treatment in the EP0009 study until the date of last dose of LCM in EP0009).

For the calculation of variables related to seizure frequency, the dates during participation in EP0024 will be considered as not done for the purpose of efficacy analyses for trial EP0009 (eg, these dates will not be considered as days evaluated for seizure frequency). Due to the short nature of the EP0024 study, only a few days of seizure frequency data are expected to be missing

due to participation in EP0024 unless otherwise specified (eg, for the evaluation of seizure freedom).

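### Section 9.3.2 lets a seizure-free run cross the EP0024 days whatever EP0024 recorded, so a run that depends on that gap can be reported as seizure-free despite a recorded seizure

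*SAP*

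**What the plan says.** Section 9.3.2 assesses seizure-free status over at least 182 and at least 365 consecutive days. The source is the EP0009 diary: "Seizure-free is defined as a report of no seizures in the seizure diary on the CRF for the consecutive days" on which the subject was treated with LCM. Diary days marked as not done "will not be counted as a seizure free day unless otherwise noted". An exception follows for EP0024: its days are also not done, but "they should not disqualify a subject from being seizure free if they were in EP0024".

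Section 4.2 gives the background. Subjects in EP0024 "will have missing data for seizure frequency and drug dosing while participating in the EP0024 trial". It continues: "As the duration of the EP0024 study will be short (3-7 days), no imputation for data missing due to participation in EP0024 will be performed". It also says that "the dates during participation in EP0024 will be considered as not done for the purpose of efficacy analyses for trial EP0009", and it names seizure freedom as a case that may be handled differently. Section 9.3.2 supplies that handling.

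Section 2.3 says that EP0024 is open to Japanese subjects at selected sites and requires hospitalization, and that its adverse events and concomitant treatments are recorded in EP0024. It adds: "All other data reported for EP0024 will be captured in the EP0024 database".

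**The concern.** Section 4.2 justifies its handling by the shortness of the gap. That works for seizure frequency, where leaving out a few days hardly moves a rate. Seizure freedom over consecutive days is all-or-nothing, and one seizure on one day decides it.

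Bridging a short unobserved gap is a reasonable convention. As worded, though, the bridge also covers a gap for which the sponsor may hold evidence of a seizure, because the status is read only from the EP0009 diary and nothing sends the programmer to the EP0024 data. What is at stake is a wrong statement about an individual subject, and a seizure-free count that can be too high but never too low. Only Japanese subjects can enter EP0024, so in the by-country tables any excess falls in the Japanese results and, through them, in the overall column.

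**Working it through.** The plan states no figure to reproduce. The check applies the rule to constructed subjects and then bounds the chance of the event.

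**Inputs from the SAP.** Required runs are 182 and 365 days (Section 9.3.2). The gap is 3 to 7 days (Section 4.2). EP0024 data sit in the EP0024 database (Section 2.3).

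**Step 1: the rule, day by day.** A diary day with a seizure resets the run to zero, a diary day without one adds 1, and an EP0024 day neither adds nor resets. The SAP does not say whether EP0024 days count toward the 182 or 365; here they are taken not to, and the result does not depend on this. Each constructed subject has no diary seizures and one seizure on the first EP0024 day.

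| Diary days before + gap + diary days after | Longest run, rule as written | Longest run if a recorded EP0024 seizure ends it |
|---|---|---|
| 91 + (3 or 7) + 91 | 91 + 91 = 182: 6-month status yes | 91: 6-month status no |
| 182 + (3 or 7) + 183 | 182 + 183 = 365: 12-month status yes | 183: 12-month status no |

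In the second row the subject still meets the 6-month criterion without any bridge, since 183 ≥ 182. Only the 12-month status is wrong.

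**Step 2: when the status changes.** Let *a* and *b* be the seizure-free diary days immediately before and after the gap, and *W* the required run. The status depends on the bridge only if a < W, b < W and a + b ≥ W, and no other stretch of follow-up supplies a run of *W* days. If a ≥ W or b ≥ W, the subject has a true qualifying run whatever happened in EP0024.

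**Step 3: chance of a seizure in the gap.** The SAP gives no seizure rate, so the rates *r* (seizures per 28 days) and a Poisson process are assumptions. For a gap of *d* days the chance of at least one seizure is 1 − exp(−r·d/28). The chance of a clean 182-day window is exp(−r·182/28) = exp(−6.5r).

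| Assumed r | d = 3 | d = 7 | Clean 182-day window |
|---|---|---|---|
| 0.1 | 1 − exp(−0.0107) = 1.1% | 1 − exp(−0.025) = 2.5% | exp(−0.65) = 52% |
| 0.25 | 1 − exp(−0.0268) = 2.6% | 1 − exp(−0.0625) = 6.1% | exp(−1.625) = 20% |
| 1 | 1 − exp(−0.107) = 10.2% | 1 − exp(−0.25) = 22.1% | exp(−6.5) = 0.15% |

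The last row is not usable as an estimate. At 1 seizure per 28 days, a subject would almost never have the clean diary days needed on either side of the gap. The first two rows give the relevant range, about 1% to 6%.

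**The case against.** The strongest reply is that the clause is a deliberate and disclosed missing-data convention. It follows directly on the rule for not-done days and is most naturally read as saying that missing diary days alone should not end a run. It does not expressly tell the analyst to ignore a known seizure. That is a fair reading of intent. But the SAP provides no route by which an EP0024 seizure could count, so the rule applied as written gives the result in Step 1.

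The second reply is that nothing in the SAP says EP0024 collects seizures or treats a habitual seizure as an adverse event. This stands. A reader might infer that the sponsor certainly holds such a record. The SAP supports only that adverse events, concomitant treatments and other EP0024 data are kept in that database, so the point is conditional on a seizure being identifiable there.

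Third, a reader might infer that every subject with a seizure during EP0024 is misclassified. That is not so. EP0009 is planned to last 3 years (Section 3.2.3), and a qualifying run wholly before or after the gap makes the status correct.

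Finally, the consequence is limited. Seizure-free status is listed among the other efficacy variables (Section 2.2.2.3), no primary efficacy variable is defined, efficacy is evaluated descriptively (Section 9), and no test compares Japan with China. All of this stands and sets the severity.

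**Conclusion.** The point holds in a narrow form and is minor. The bridge in Section 9.3.2 lacks a condition. A subject is wrongly reported as seizure-free only if three things coincide: participation in EP0024, a run that reaches 182 or 365 days only by crossing the gap, and a seizure recorded in EP0024 as a seizure record, an adverse event or a medication given for a seizure.

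The effect on the seizure-free percentage cannot be computed, because neither the number of EP0024 participants nor what EP0024 records about seizures is given. For a subject with a bridge-dependent run, the chance of a seizure in the gap is about 1-6%, assuming a Poisson process with 0.1-0.25 seizure per 28 days. The chance of a misclassification is no higher than that, since the seizure must also have been recorded. The direction is certain: the error can only raise the count. A figure near 22% might be inferred from higher rates, but those rates are not compatible with long seizure-free stretches around the gap. The decision to bridge a short unobserved gap is not itself at fault.

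**What to change.** In Section 9.3.2, replace the unconditional clause with wording such as: *Days in EP0024 do not break a seizure-free run unless a seizure is recorded for the subject in the EP0024 database (as a seizure record, an adverse event, or a medication given for a seizure); in that case the run ends on that date.*

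In the by-subject seizure-freedom listing that Section 9.3.2 already plans, flag each run that qualifies only by crossing EP0024 days. If EP0024 proves to hold no seizure information, also give the 6- and 12-month counts without the bridge-dependent subjects, so that the reader sees how much rests on the convention.

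The cost is one cross-database check, including a decision on which adverse events or medications denote a seizure, and possibly a slightly lower seizure-free count.
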